1.2 Study rationale

The majority of COPD patients in the Russian Federation seek medical attention from primary care physicians at outpatient polyclinic institutions. Physicians of these institutions can refer a patient for spirometric testing or to a pulmonologist (in this case, as a general rule, spirometry is also performed).

In the recent years in Europe registries of COPD patients have been created: Registry of COPD phenotypes in patients in Central and Eastern Europe (POPE Study- Phenotypes of COPD in Central and Eastern Europe) 2014-2015, Czech multicentre registry of COPD patients, started in 2014 (Czech Multicentre Research Database of COPD, Novotná et al. Czech multicenter research database of severe COPD. International Journal of Chronic Obstructive Pulmonary Disease 2014, 9: 1265-1274".)

Registry of COPD patients includes monitoring of the possible causes of the disease, prevalence of different phenotypes, assessment of disease progression, therapeutic approaches to disease treatment in real-life clinical practice, analysis of social and economical disease burden.

It is an important clinical and economical goal to arrange a registry of COPD patients who undergo outpatient surveillance at polyclinic institutions of Moscow, including description of patient clinical profile, diagnosis flow chart, therapeutic treatment tactics using different groups of medicinal products, compliance of used diagnostic and therapeutic approaches with current Federal clinical guidelines for COPD diagnosis and treatment, evolution of COPD prevalence parameters, monitoring of course of the disease.

In the absence of this information it is impossible to evaluate the quality of medical care provided to COPD patients in the Russian Federation or to plan any actions for treatment refinement.

Therefore, the purposes of the present study result from the necessity to perform the following:

- a) evaluate therapeutic trends in an outpatient polyclinic setting for patients with diagnosed COPD,
- b) define clinical profile of COPD patients seeking attention and/or present in outpatient polyclinic medical care of healthcare system of Moscow (including diagnosis and therapeutic treatment tactics using different therapy regimens).
- c) determine the extent of the therapy conducted and its compliance with diagnosis, disease severity and phenotype
- d) define the disease burden (number of outpatient visits, hospitalizations, disability)

Investigation of the management of COPD patients in real-life clinical practice will enable us to obtain demographic and social data of the patients, study the natural history of COPD, evaluate the efficacy of therapy, demand for specialized treatment, perform pharmacoeconomic analysis, and develop standard statistical forms.

2. STUDY OBJECTIVES

2.1. Primary study objective

1. To describe the clinical profile of COPD patient who is under outpatient surveillance at polyclinic institutions of Moscow (including demographic data (age, gender, ethnicity, occupation), smoking status, disease duration, disease severity grade, distribution by disease phenotype, disease exacerbation rate in the setting of real-life clinical practice)

2.2. Secondary objectives

1. Characterize distribution (percentage (%)) of COPD patients who seek attention from primary medical care physicians by severity of airway obstruction, by reversibility of airway obstruction according to criteria described in Federal clinical guidelines for COPD diagnosis and treatment 2014
2. To determine prevalence of the different disease phenotypes among outpatients: chronic bronchitis phenotype, emphysema phenotype, mixed phenotype, frequent exacerbator phenotype, Asthma+COPD phenotype (according to criteria described in Federal clinical guidelines for COPD diagnosis and treatment 2013)
3. To determine the percentage of patients with eosinophilic inflammation according to haematology results
4. To describe treatment regimens prescribed to COPD patients depending on disease severity grade in the setting of real-life clinical practice

5. To establish the percentage of medical prescriptions for treatment of COPD patients which comply with current Federal clinical guidelines for diagnosis and treatment of chronic obstructive pulmonary disease
6. To establish prevalence and pattern of comorbidities in COPD patients
7. To evaluate the disease burden based on the collected data concerning the duration of temporary disability, number of hospitalizations due to COPD exacerbations, number of outpatient visits concerning COPD patients under outpatient surveillance at polyclinic institutions of Moscow for three years

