9. Disease burden based on the collected data concerning the duration of temporary disability, number of hospitalizations due to COPD exacerbations, outpatient visits concerning COPD during follow-up

Statistics

Descriptive analysis approach will be applied for analysis of the study objectives. Descriptive statistics will be used for analysis of the study population, baseline and clinical data.

Descriptive statistics will include frequency tables (n, mean, median, standard deviation, minimum and maximum for continuous variables; n, frequency and percentage for categorical variables). Percentages will be evaluated together with 95% confidence intervals (in appropriate cases).

TABLE OF CONTENTS

	PAGE
TITLE PAGE	1
PROTOCOL SYNOPSIS	2
TABLE OF CONTENTS	8
LIST OF ABBREVIATIONS	11
1. INTRODUCTION	12
1.1 Background	12
1.2 Study rationale	13
2. STUDY OBJECTIVES	14
2.1 Primary study objective	14
2.2 Secondary objectives	14
3. STUDY PLAN AND PROCEDURES	15
4. PATIENT POPULATION	17
4.1 Physicians-investigators	17
4.2 Selection criteria for COPD patients	18
4.2.1 Inclusion criteria for patients with diagnosed COPD	18
4.2.2 Exclusion criteria for patients with COPD risk factors and for patients with previously diagnosed COPD	18
5. PATIENT WITHDRAWAL FROM THE STUDY	18
5.1 Withdrawal criteria	18
5.2 Procedures for patient withdrawal from the study	18
6. PATIENT TREATMENT	19
6.1 Treatment strategy in observational studies	19
7. STUDY CONDUCTION	19
7.1 Description of the visits	19
8. PARAMETERS COLLECTED FOR STUDY, ASSESSMENT AND REGISTRATION METHODS	20
8.1 Primary endpoints	20
8.2 Secondary endpoints	20
8.3 Economic health assessment	21
8.3.1 Disease burden assessment	21
8.3.2 Other parameters for disease burden assessment	21
9. SAFETY ASSESSMENT	21
9.1 Definitions	21

Number/Code:
Version:
Date:

9.1.1	Definition of an adverse event (AE).....	21
9.1.2	Definition of a serious adverse event (SAE).....	22
9.2	Non-interventional studies without specific safety assessment objectives	22
9.3	Non-interventional studies with specific safety assessment objectives	22
9.4	Safety data reporting	23
9.4.1	Adverse event reports.....	23
9.4.2	Reports of unexpected adverse events during use of medicinal products for human use.....	23
9.4.3	Registration of spontaneous reports regarding adverse events	23
10.	ETHICS	24
10.1	Committee on ethical review for clinical studies (EC)	24
10.2	Informed consent.....	24
10.3	Patient data confidentiality	24

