Physicians-investigators will enter into the study the information (data) concerning COPD patients, both those already registered at the selected medical treatment and preventive care institution, and newly registered patients as they seek attention at the outpatient polyclinic institutions during the registry conduction period.

The main purpose of the present study consists in collection of data concerning COPD patients under surveillance at outpatient polyclinic institutions of Moscow using patient medical records and their medical history. This protocol does not specify any obligatory visits or examinations.

Patient data will be entered into the registry de-identified. The patients will be identified by their screening number and initials. Then the Physician-investigator will evaluate patient compliance with inclusion criteria. The study will enrol patients meeting all the inclusion criteria and not having any of the exclusion criteria.

Only the physician who enters patient data into the regional COPD registry possesses patient contact information, and henceforth only this physician will enter de-identified patient data according to study design. This physician does not influence the choice of examination extent, treatment strategy and medication.

Visit "Enrolment". At this visit de-identified data of the patients will be included into the study. De-identified data are entered retrospectively based on analysis of the outpatient medical records.

At this visit the Physician-investigator will complete the following information (collected retrospectively):

1. Verify inclusion/ exclusion criteria
2. Establish the date of COPD diagnosis
3. Collect medical history concerning significant comorbidities and clinical characteristics, rate of exacerbations, pneumonia cases, hospitalizations, number of outpatient visits concerning COPD, number of days of disability in the year prior to enrolment
4. Evaluate smoking status. Wherever possible, smoking in pack-years
5. Collect medical history concerning treatment regimens, including different regimens of CS use, which the patient took/was prescribed in the year prior to enrolment into the registry (trade name of the medicinal product and INN, doses, dosing regimen, duration of use)
6. Collect demographic data and information concerning the patient's socioeconomic status

Number/Code:
Version:
Date:

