7. Collect data concerning the results of laboratory tests and instrumental examination methods confirming COPD diagnosis, present in the outpatient medical records (spirometry, specific complaints, haematology, instrumental examination methods)
8. Determine the patient's phenotype according to current classification
9. Collect data concerning adverse drug reactions
10. Complete the CRF.

Table 1. Visit schedule

Procedures	Visit "Enrolment"
Timelines	At the moment of enrolment into the registry
Inclusion / exclusion criteria	X
COPD. Severity grade, reversibility of airway obstruction (according to spirometry results*)	X
Demographics (year of birth, ethnicity, gender),	X
Socioeconomic status (education, occupation)	X
Smoking status	X
Occupational status, including information regarding the number of days of disability in the past 1 year.	X
Height, Weight, BMI (if applicable)	X
Comorbidities and clinical characteristics	X
Number of exacerbations COPD	X
Number of outpatient visits concerning COPD per year	X
Mean number of hospitalizations due to COPD	X
Determination of patient's phenotype according to current classification	X
Medical history concerning prior treatment of COPD	X
Medical history concerning treatment of COPD in the year prior to enrolment	X
Collection of data regarding changes in regimens of COPD treatment in the year prior to enrolment	X
Information concerning new complaints	
Spirometry. Results evolution (if applicable*)	X
Chest X-ray examination (if applicable*)	X*
Eosinophilia (eosinophil blood count based on haematology (Data of Le, EOS in % and in cells per μ l (haematology)	X
Pulse oximetry (if applicable*)	X*
Adverse drug reactions	X
CRF completion	

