8.2 Secondary endpoints

1. Percentage (%) of patients with different disease phenotypes among outpatients
2. Percentage (%) of prescriptions of medicinal products to COPD patients which are in line with their disease severity according to Federal clinical guidelines for diagnosis and treatment of COPD patients, 2014
3. Distribution (%) of COPD patients who seek attention from primary medical care physicians by severity of airway obstruction (according to Federal clinical guidelines for diagnosis and treatment of COPD patients, 2014)
4. Mean number of exacerbations requiring medical attention (outpatient prescription of oral corticosteroids CS and/or antibiotics) in the last year in COPD patients
5. Mean number of hospitalizations in the last year in COPD patients
6. Mean duration (seriousness) of a temporary disability case. Number of days of temporary disability /Number of cases of temporary disability (reference form 16-BH)
7. Percentage (%) of COPD patients who received different regimens for treatment of COPD, including short-acting muscarinic antagonist (SAMA), short-acting β_2 -agonists (SABA), long-acting β_2 -agonists (LABA), long-acting muscarinic antagonist (LAMA),

oral corticosteroids (oral CS), fixed dose combination (FDC), phosphodiesterase-4 inhibitor, theophylline for the past year

8. Percentage (%) prescriptions to COPD patients which are in line with their disease severity according to GOLD classification and Federal clinical guidelines for treatment choice
9. Percentage (%) of patients with eosinophilic inflammation (eosinophil count according to haematology $>2\%$, $>3\%$, $>4\%$ or equivalent to absolute counts of >200 , >300 , >400 cells per μl)
10. Percentage of patients receiving sufficient extent of treatment in line with disease severity according to Federal clinical guidelines for diagnosis and treatment of COPD patients, 2014
11. Disease burden based on the collected data concerning the duration of temporary disability, number of hospitalizations due to COPD exacerbations, outpatient visits concerning COPD during follow-up

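### Objective 7 speaks of disease burden for three years and endpoint 11 of an undefined follow-up, but the only collection described looks back one year from enrolment

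*Combined protocol and SAP*

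**What the plan says.** **Objective.** Item 7 of section 2.2, repeated in the synopsis, evaluates burden from the duration of temporary disability, hospitalizations for exacerbations, and the "number of outpatient visits concerning COPD patients under outpatient surveillance at polyclinic institutions of Moscow for three years".

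**Endpoint.** Item 11 of sections 8.2 and 12.2 (item 9 of the synopsis variables) lists the same three items and closes with "outpatient visits concerning COPD during follow-up". No section gives a start, a length or an end for follow-up. Sections 8.3 to 8.3.2, on burden, give no window either.

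**Collection.** Sections 3 and 7.1 describe one visit, Enrolment. Its item 3 is a list that includes exacerbations and hospitalizations and ends with "number of outpatient visits concerning COPD, number of days of disability in the year prior to enrolment". Table 1 has a single column, for that visit. Its burden rows are:
- "Occupational status, including information regarding the number of days of disability in the past 1 year", which states one year;
- "Number of outpatient visits concerning COPD per year", which states a yearly unit;
- "Mean number of hospitalizations due to COPD", which states no window.

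Endpoint 5 supplies a window for hospitalizations: "Mean number of hospitalizations in the last year in COPD patients".

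**Text pointing the other way.** The synopsis and section 3 say that the registry rests on a regular yearly review of patient records. That review appears neither in Table 1 nor in section 7.1.

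**The concern.** The objective, its endpoint and the data collection give three different periods for the same quantities: three years, an undefined follow-up, and one year. A report built on the scheduled data would present one-year figures under an objective that most readers will take to mean three.

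The gap could also be filled informally from the yearly review. Patients would then contribute different lengths of observation. The planned statistics (synopsis, and section 12.4) are descriptive summaries without a person-time denominator, so mean numbers of visits, hospitalizations or disability days would mix unequal exposure and could not be compared with a three-year or a one-year figure.

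**Working it through.** There is no sample-size or power figure to reproduce: section 12.5 says that none was calculated, and this point does not need one. The check is calendar arithmetic.

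**Inputs**
- Stated period: three years = 36 months (section 2.2, objective 7).
- Scheduled look-back: 12 months (sections 3 and 7.1, item 3).
- First patient enrolled Q4 2016, last patient enrolled Q2 2018, database lock Q4 2018 (section 10.5).
- Last patient out Q3 2018 (synopsis timeline).

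**1. Scheduled collection only.** 12 / 36 = 33%, which leaves 36 − 12 = 24 months per patient uncovered, if three years is the per-patient burden window.

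**2. Adding the yearly review.** Assume that it extracts the burden items without gaps up to a cut-off. The documents state neither the items nor the cut-off. Then

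total window = 12 + months from enrolment to cut-off.

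The ranges run from the shortest to the longest interval that the stated quarters allow.

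| Enrolled | To last patient out (Q3 2018) | To database lock (Q4 2018) |
|---|---|---|
| Q4 2016 | 12 + (18 to 24) = 30 to 36 | 12 + (21 to 27) = 33 to 39 |
| Q2 2018 | 12 + (0 to 6) = 12 to 18 | 12 + (3 to 9) = 15 to 21 |

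**3. Share of patients reaching 36 months.** A patient needs 24 months between enrolment and cut-off. Take the widest dates (enrolment from 1 October 2016 to 30 June 2018, which is 21 months) and even accrual, which is an assumption.
- Cut-off 30 September 2018: enrolment by 30 September 2016 would be needed, before the first planned enrolment, so the share is essentially 0.
- Cut-off 31 December 2018: enrolment by 31 December 2016, so 3 / 21 = 14%.

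**4. Unequal exposure.** In the last case the first patient has 12 + 27 = 39 months and the last has 12 + 6 = 18, a ratio of 39 / 18 ≈ 2.2. The mean is (39 + 18) / 2 = 28.5 months.

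**5. Calendar span of the look-backs.** From the start of the first one-year look-back to the end of the last is 12 + (15 to 21) = 27 to 33 months. This also falls short of 36.

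**The case against.** **Three years may not be the burden window.** In objective 7 the phrase follows the words about surveillance and can be read as describing how long the patients had been under it. That reading is grammatical, and under it one-year data could answer the objective. A reader might therefore infer too much from a flat statement that the objective cannot be met: the 33% is conditional. Nothing else supports the alternative, however. Section 4.2.1 sets no minimum time under surveillance, and section 3 admits newly registered patients. It also leaves endpoint 11 without a defined follow-up. Reading three years as the registry's calendar span does not fit either (step 5).

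**The one-year phrase closes a list.** It might apply to disability days only. Reading it across the list is likelier, and endpoint 5 agrees for hospitalizations. If it did apply to disability days alone, hospitalizations would have no stated collection window.

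**Table 1 may be incomplete as read.** The rows on new complaints and on completing the CRF carry no mark. The conclusion therefore rests on sections 3 and 7.1, which describe no second visit.

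**Longer observation is possible.** A reader might infer that no patient could reach three years. The documents do not support that. Extraction to database lock would take some early patients past 36 months, and because section 10.2 describes archival data, a look-back longer than a year could be feasible for patients already registered. Neither is planned in the text: no section schedules such extraction or states its window.

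**Conclusion.** The inconsistency stands. Objective 7, endpoint 11, the yearly-review text and the Enrolment visit do not state one observation period, and endpoint 11 relies on a follow-up that is not defined under any reading.

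On the likelier reading, the scheduled data cover one third of the stated period. The unscheduled yearly review would not close the gap for most patients: with a 12-month look-back, gap-free extraction to the end of Q4 2018 and even accrual at the widest dates, about 14% would reach 36 months. That percentage illustrates the timeline and is not a bound, because it depends on all of these assumptions.

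The reach is limited to one of seven secondary objectives and its endpoint. The primary objective is unaffected.

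**What to change.** **Preferred.** Restate objective 7 (synopsis and section 2.2) and endpoint 11 (synopsis variable 9, sections 8.2 and 12.2) as burden in the 12 months prior to enrolment, and print that window in the hospitalizations row of Table 1. This needs no new data. Its costs are a burden claim that narrows from three years to one, and written ethics approval before the amendment takes effect (section 10.1).

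**Only if the sponsor does intend data beyond that year**, whether from post-enrolment review or from a longer archival look-back: schedule the extraction in Table 1 with its items and end date, record each patient's observed time, and report burden as rates per person-year rather than as three-year totals or simple means. This costs a further record extraction for patients already enrolled, as well as the same ethics approval.

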3. STUDY PLAN AND PROCEDURES

The registry of COPD patients represents a non-interventional multicenter descriptive retrospective study of all COPD patients, which medical records will be retrospectively added to the registry database and newly diagnosed under outpatient surveillance at the selected polyclinic institutions of Moscow with retrospective entry of data.

it will include all patients with registered diagnoses J40 - J44 according to ICD-10 with spirometry results confirming COPD diagnosis, who are at the study start under outpatient surveillance, and also newly registered patients diagnosed with COPD (ICD-10 J40 - J44, as confirmed by spirometry results) during the conduction of the registry program at the selected polyclinic institutions of Moscow (according to ICD: J40 - Bronchitis, not specified as acute or chronic, J41 - Simple and mucopurulent chronic bronchitis, J41.0 - Simple chronic bronchitis, J41.8 - Mixed simple and mucopurulent chronic bronchitis, J 42 - Unspecified chronic bronchitis, J 43 - Emphysema, J 44 - Other chronic obstructive pulmonary disease) based on regular (yearly) retrospective analysis of patient records with data entry into a consolidated database.

It is planned to enrol into the study approximately **2000** male and female patients over 40 years of age with diagnosed COPD (as confirmed by spirometry results).

The present observational multicenter descriptive study will be conducted in the setting of routine clinical practice of outpatient polyclinic institutions. There is no hypothesis to be tested in this study.

The study will be conducted in outpatient polyclinic institutions of the primary medical care system of Moscow. Pulmonologists of the primary medical care system will be engaged as investigators. These are the physicians, whom the patients with tentative COPD diagnosis are referred to in the Russian Federation and who within the scope of their responsibilities have access to source medical records and who evaluate the quality of diagnosis and extent of treatment prescribed to COPD patients.

The present study is observational therefore it does not require a treatment regimen or directions for patient management. The patients receive medical care in line with routine practice for treatment of this disease in the Russian Federation. Patient participation in the

study should not in any way affect the principles and extent of treatment received by the patient according to routine clinical practice.

Physicians-investigators will enter into the study the information (data) concerning COPD patients, both those already registered at the selected medical treatment and preventive care institution, and newly registered patients as they seek attention at the outpatient polyclinic institutions during the registry conduction period.

The main purpose of the present study consists in collection of data concerning COPD patients under surveillance at outpatient polyclinic institutions of Moscow using patient medical records and their medical history. This protocol does not specify any obligatory visits or examinations.

Patient data will be entered into the registry de-identified. The patients will be identified by their screening number and initials. Then the Physician-investigator will evaluate patient compliance with inclusion criteria. The study will enrol patients meeting all the inclusion criteria and not having any of the exclusion criteria.

Only the physician who enters patient data into the regional COPD registry possesses patient contact information, and henceforth only this physician will enter de-identified patient data according to study design. This physician does not influence the choice of examination extent, treatment strategy and medication.

Visit "Enrolment". At this visit de-identified data of the patients will be included into the study. De-identified data are entered retrospectively based on analysis of the outpatient medical records.

At this visit the Physician-investigator will complete the following information (collected retrospectively):

1. Verify inclusion/ exclusion criteria
2. Establish the date of COPD diagnosis
3. Collect medical history concerning significant comorbidities and clinical characteristics, rate of exacerbations, pneumonia cases, hospitalizations, number of outpatient visits concerning COPD, number of days of disability in the year prior to enrolment
4. Evaluate smoking status. Wherever possible, smoking in pack-years
5. Collect medical history concerning treatment regimens, including different regimens of CS use, which the patient took/was prescribed in the year prior to enrolment into the registry (trade name of the medicinal product and INN, doses, dosing regimen, duration of use)
6. Collect demographic data and information concerning the patient's socioeconomic status

Number/Code:
Version:
Date:

7. Collect data concerning the results of laboratory tests and instrumental examination methods confirming COPD diagnosis, present in the outpatient medical records (spirometry, specific complaints, haematology, instrumental examination methods)
8. Determine the patient's phenotype according to current classification
9. Collect data concerning adverse drug reactions
10. Complete the CRF.

Table 1. Visit schedule

Procedures	Visit "Enrolment"
Timelines	At the moment of enrolment into the registry
Inclusion / exclusion criteria	X
COPD. Severity grade, reversibility of airway obstruction (according to spirometry results*)	X
Demographics (year of birth, ethnicity, gender),	X
Socioeconomic status (education, occupation)	X
Smoking status	X
Occupational status, including information regarding the number of days of disability in the past 1 year.	X
Height, Weight, BMI (if applicable)	X
Comorbidities and clinical characteristics	X
Number of exacerbations COPD	X
Number of outpatient visits concerning COPD per year	X
Mean number of hospitalizations due to COPD	X
Determination of patient's phenotype according to current classification	X
Medical history concerning prior treatment of COPD	X
Medical history concerning treatment of COPD in the year prior to enrolment	X
Collection of data regarding changes in regimens of COPD treatment in the year prior to enrolment	X
Information concerning new complaints	
Spirometry. Results evolution (if applicable*)	X
Chest X-ray examination (if applicable*)	X*
Eosinophilia (eosinophil blood count based on haematology (Data of Le, EOS in % and in cells per μ l (haematology)	X
Pulse oximetry (if applicable*)	X*
Adverse drug reactions	X
CRF completion	

